11.4.2. Additional Reporting Requirements for Suspected Unexpected Serious Adverse Reaction

Any AE that is serious, unexpected, and associated with the use of study treatment (SUSAR, also referred to as Expedited Safety Report, Investigational New Drug Safety Report), has additional reporting requirements. All investigators conducting clinical trials with the study treatment will be notified of such events and must inform their IRBs/ECs as required in accordance with local law. Amicus will ensure SUSARs are reported to regulatory agencies in accordance with local law in each country where study sites are located.

- If the SUSAR is fatal or life-threatening, associated with the use of study treatment, and unexpected, regulatory authorities and IRBs/ECs will be notified within 7 calendar days after Amicus learns of the event.
- If the SUSAR is not fatal or life-threatening but is otherwise serious, associated with the use of study treatment, and unexpected, regulatory authorities and IRBs/ECs will be notified within 15 calendar days after Amicus learns of the event.

Safety updates will be provided periodically to the regulatory authorities and IRBs/ECs responsible for the study according to the rules in effect in each country where study sites are located. These updates will include information on SUSARs and other relevant safety findings.

11.4.3. Additional Reporting Requirements for Serious Adverse Reaction

For subjects in this study that participate at more than one study site, Amicus drug safety personnel will forward a copy of the initial SAE report to any alternate site(s) attended by the subject. When all information related to the SAE is available, a MedWatch form will be sent to all sites at which the subject participates.

If additional information such as medical history (inclusive of FVC and 6MWT, plasma CK, ALT, AST, and urine Hex4 lab results) is obtained from the report or from a hospital discharge summary, the data should be reconciled by the primary site (site conducting Functional Assessment) and recorded in the eCRF accordingly.

11.5. Study Treatment Interruptions/Discontinuation Due to an Adverse Event

Investigators may choose to discontinue subjects from the study in the case of an AE or for administrative reasons. All discontinuations must be documented in the eCRF with the appropriate source documents and communicated to the Amicus Medical Monitor immediately.

If the reason for discontinuation of the study is an abnormal assessment (eg, ECG finding) or a laboratory test abnormality, the information must be recorded as an AE in the eCRF and source records.

11.6. Other Reporting Situations

11.6.1. Pregnancy

Pregnancy in and of itself is not regarded as an AE; however, pregnancy information on female subjects and female partner of male subjects, participating in this study, is collected by Amicus.

If a female subject becomes pregnant during the course of this study, or if the female partner of a male subject becomes pregnant during the subject's participation in the study, must be reported using Amicus' pregnancy notification form (subject to receipt of any data privacy release approvals where required under local privacy laws) within 5 working days of the investigator or study staff becoming aware of the pregnancy. If an SAE occurs in conjunction with the pregnancy, the same SAE reporting requirements described in Section 11.4.1 apply. Instructions regarding collection of pregnancy and outcome information will be provided by Amicus.

11.6.2. Overdose/Underdose

Any event associated with, or observed in conjunction with, a product overdose/under dose (whether accidental or intentional) is considered by Amicus to be an AE and must be reported as such. If a subject experiences an overdose (defined as $\geq 20\%$ higher than the assigned dose of study treatment for that period in the protocol) or an underdose (defined as $\geq 20\%$ lower than the assigned dose of study treatment for that period in the protocol) during the course of the study (whether symptomatic or not), Amicus Medical Monitor must be notified within 5 working days of the investigator or study staff first becoming aware of the overdose. Follow-up information must be forwarded on the outcome as applicable. If an SAE occurs in conjunction with the overdose, the same SAE reporting requirements described in Section 11.4.1 apply.

If a subject is unable to schedule a treatment (infusion) up to 7 days after the actual scheduled date, this is considered as a missed dose. The subject will receive the next dose per his/her schedule. In this case, the interval between 2 doses will be approximately 4 weeks. This is recorded as a protocol deviation and an adverse event. Amicus Medical Monitor must be notified within 5 working days of the investigator or study personnel first becoming aware of the missed dose. Follow-up information must be forwarded on the outcome as applicable. If an SAE occurs

in conjunction with the underdose, the same SAE reporting requirements described in Section [11.4.1](#) apply.

12. DATA ANALYSIS AND STATISTICAL CONSIDERATIONS

This section outlines the planned statistical analyses. Further details of the data handling rule and statistical calculations will be provided in a separate statistical analysis plan (SAP).

12.1. Endpoints

12.1.1. Primary Endpoints

Safety:

- Identification and counts of TEAEs, treatment-emergent SAEs, including IARs
- Changes from baseline in 12-lead ECG
- Changes from baseline in clinical safety laboratory evaluations: serum chemistry, hematology, and urinalysis
- Changes from baseline in PEs
- Changes from baseline in vital signs
- Changes from baseline in serum CK

PK for subjects from Cohort 1:

- Plasma GAA activity levels and total GAA protein concentration PK parameters: C_{max} , t_{max} , AUC_{0-t} , $AUC_{0-\infty}$, $t_{1/2}$, steady state volume of distribution (V_{ss}), and CL_T for each dose level
- Stage 1: Ratios of plasma GAA activity levels and total GAA protein concentration C_{max} , AUC_{0-t} , and $AUC_{0-\infty}$ for 20 mg/kg versus 5 mg/kg, 20 mg/kg versus 10 mg/kg, and 10 mg/kg versus 5 mg/kg
- Stage 2: Ratios of plasma GAA activity levels and total GAA protein concentration C_{max} , AUC_{0-t} , and $AUC_{0-\infty}$ for 20 mg/kg ATB200 (from Stage 1) versus single-dose 20 mg/kg ATB200 + 130 mg AT2221, and versus single-dose 20 mg/kg ATB200 + 260 mg AT2221
- Stage 2: Ratios of plasma GAA activity levels and total GAA protein concentration C_{max} , AUC_{0-t} , and $AUC_{0-\infty}$ for 20 mg/kg ATB200 + 130 mg AT2221 single-dose versus multiple-dose, and 20 mg/kg ATB200 + 260 mg AT2221 single-dose versus multiple-dose
- Plasma AT2221 PK parameters: C_{max} , t_{max} , AUC_{0-t} , $AUC_{0-\infty}$, $t_{1/2}$, total clearance following oral administration (CL_T/F), and terminal phase volume of distribution following oral administration (V_z/F) for each dose level
- Ratios of plasma AT2221 C_{max} , AUC_{0-t} , and $AUC_{0-\infty}$ for 260 mg single-dose versus 130 mg single-dose, and for 260 mg multiple-dose versus 130 mg multiple-dose
- Ratios of plasma AT2221 C_{max} , AUC_{0-t} , and $AUC_{0-\infty}$ for 130 mg multiple-dose versus 130 mg single-dose, and 260 mg multiple-dose versus 260 mg single-dose

12.1.2. Secondary Endpoints

Functional:

- For ambulatory subjects: change and percent change from Baseline in Gower's Maneuver, 4-stair-climb, 6MWT, 10-Meter Walk Test (10MWT), GSGC score, TUG, muscle strength tests (MRC and hand-held dynamometer [for both upper and lower limbs]), and pulmonary function tests (FVC, MIP, MEP, and SNIP [for subjects without invasive ventilatory support])
- For nonambulatory subjects: change and percent change from Baseline in muscle strength tests (MRC and hand-held dynamometer [upper limbs only]) and pulmonary function tests (FVC, MIP, MEP, and SNIP [for subjects without invasive ventilatory support])

Patient-reported Outcomes:

- Change and percent change from Baseline in FSS, RHS, and R-PAct Scale

Global Impression of Change:

- PGIC and SGIC

PK parameters for subjects from Cohorts 1 and 3:

- Plasma GAA activity levels and total GAA protein concentration PK parameters: C_{max} , t_{max} , AUC_{0-t} , $AUC_{0-\infty}$, $t_{1/2}$, CL_T and V_{ss}
- Plasma GAA activity levels and total GAA protein concentration ratios for C_{max} , AUC_{0-t} , and $AUC_{0-\infty}$ for single-dose versus multiple-dose
- Plasma AT2221 PK parameters: C_{max} , t_{max} , AUC_{0-t} , $AUC_{0-\infty}$, $t_{1/2}$, CL_T/F , and V_z/F
- Plasma AT2221 C_{max} , AUC_{0-t} , and $AUC_{0-\infty}$ ratios for single-dose versus multiple-dose
- Single-dose plasma GAA activity levels, total protein concentration and AT2221 C_{max} , AUC_{0-t} , and $AUC_{0-\infty}$ ratios for subjects from Cohort 3 versus subjects from Cohort 1 following 20 mg/kg ATB200 alone, 20 mg/kg ATB200 + 130 mg AT2221 single-dose, and 20 mg/kg ATB200 + 260 mg AT2221 single-dose

12.1.3. Exploratory Endpoints

- Anti-rhGAA antibodies (total and neutralizing)
- Cross-reactivity of anti-rhGAA antibodies to alglucosidase alfa
- Pro-inflammatory cytokines and other biomarkers of immune system activation
- PD biomarkers: urinary Hex4 and serum CK
- Evaluation of anti-rhGAA antibody impact on AUC and CL_T after at least 18 months of ATB200/AT2221 treatment as compared to AUC and CL_T after the first and third doses of 20 mg/kg ATB200 + 260 mg AT2221

12.2. Hypotheses

No formal statistical hypotheses are specified for this study.

12.3. Sample Size Considerations

No formal sample size calculation was performed. The sample size between 18 to 34 subjects is considered adequate for the purpose of this study.

12.4. Data Analysis Considerations

12.4.1. Analysis Populations

- Safety Population: this includes all enrolled subjects who have been exposed to at least 1 dose of study treatment (ATB200 and/or AT2221).
 - The Safety population will be used in the analysis of all safety parameters (including AEs, vital signs, laboratory assessments, and biomarkers).
- PK Analysis Population: includes enrolled subjects who have been exposed to at least 1 dose of study treatment (ATB200 and/or AT2221) and have completed at least 1 PK period.
 - The PK population will be used for PK analyses.
- Intent-to-Treat Population: includes all enrolled subjects.
- Other populations may be defined in the SAP.

12.4.2. Interim Analyses

Interim analyses will be performed in the study as needed. Full details for the interim analysis will be presented in the SAP.

12.4.3. PK/PD Analysis

12.4.3.1. Drug Concentration Data

Blood samples will be collected at serial time points specified in [Table 14](#) for plasma GAA activity, plasma total GAA protein concentration, and plasma AT2221 concentration for all subjects. Plasma GAA activity levels, total GAA protein, and AT2221 concentrations will be used to compute PK parameters defined in [Section 12.4.3.2](#).

12.4.3.2. PK Parameters

Plasma PK parameters will be computed by noncompartmental analysis with Phoenix[®] WinNonlin[®] version 6.4. For the purpose of calculating PK parameters, values below the limit of quantification (BLQ) will be set to 0 when a BLQ occurs before the first measurable concentration. If a BLQ occurs after a measurable concentration in a profile and is followed by a value above the lower limit of quantification, then the BLQ will be treated as “missing”. If a BLQ value occurs at the end of the blood sampling interval (after the last quantifiable concentration) it will also be treated as “missing”. For descriptive statistics of plasma activity

and concentration data, all BLQs will be set to 0 and included in designated statistical calculations. PK analyses performed on preliminary quality checked activity or concentration data will use nominal time points. PK analyses performed on final activity or concentration data will use actual time points. PK endpoints may include the following:

Plasma GAA activity levels and total GAA protein concentration PK parameters will be calculated as follows:

- C_{max} : Maximum observed activity level or concentration obtained directly from the activity or concentration profile
- t_{max} : Time of the first occurrence of the maximum observed activity level or concentration obtained directly from the activity or concentration profile
- K_{el} or λ_z : The apparent terminal phase elimination rate constant will be estimated by linear regression of logarithmically transformed concentration (or activity) versus time data. Only those data points which are judged to describe the terminal log-linear decline will be used in the regression.
- AUC_{0-t} : The area under the plasma drug concentration-time curve from 0 time (predose) to the time of last quantifiable concentration (t) will be calculated with the linear up/log-down trapezoidal method
- $AUC_{0-\infty}$: The area under the plasma drug concentration-time curve from 0 time (predose) extrapolated to infinite time will be calculated as follows:

$$AUC_{0-\infty} = AUC_{0-t} + C_t / \lambda_z$$

Where C_t is the last observed quantifiable concentration

- $t_{1/2\beta}$: The beta-phase terminal elimination half-life, calculated as natural log (\ln)[2]/ λ_z from the last 3 or more quantifiable concentrations from the beta phase of elimination
- $t_{1/2\alpha}$: The alpha-phase terminal half-life, calculated as $\ln(2) / \lambda_z$ from the first 3 or more quantifiable concentrations after C_{max} . Estimated for plasma GAA activity levels and total GAA protein concentration only
- CL_T : total plasma clearance after IV administration, calculated as Dose/ $AUC_{0-\infty}$
- V_{ss} : Steady-state volume of distribution from an IV administration, calculated as $Dose \cdot AUMC / (AUC)^2$, where AUMC is area under the first moment curve

Plasma AT2221 PK parameters will include the parameters listed above in addition to the following:

- CL_T/F : Total plasma clearance from an oral administration, calculated as $Dose / AUC_{0-\infty}$
- V_z/F : Volume of distribution based on the terminal elimination phase from an oral administration, calculated as $Dose / (AUC_{0-\infty} \cdot \lambda_z)$

12.4.4. Statistical Methods

12.4.4.1. Statistical Plan for PK Data

For the purpose of summarizing drug concentration/activity data, all BLQs will be set to zero (0) values. Drug concentration/activity data will be summarized with descriptive statistics including arithmetic means, standard deviations (SDs), coefficients of variation, median, minimum, and maximum, standard error of the mean, and 5th and 95th percentiles. Pharmacokinetic parameters will be summarized with descriptive statistics including N (number of subjects in the treatment population), arithmetic means, SDs, coefficients of variation, median, minimum, and maximum. Geometric means will be calculated for AUC_{0-t}, AUC_{0-∞}, and C_{max}.

The following statistical analysis of variance (ANOVA) comparisons will be performed to assess the relative bioavailability on PK parameters C_{max}, AUC_{t-0}, and AUC_{0-∞} for plasma GAA activity levels and total GAA protein concentrations:

Cohort 1 Subjects:

- 20 mg/kg ATB200 + 130 mg AT2221 (single dose) versus 20 mg/kg ATB200 alone
- 20 mg/kg ATB200 + 260 mg AT2221 (single dose) versus 20 mg/kg ATB200 alone
- 20 mg/kg ATB200 + 130 mg AT2221 (single dose) versus 20 mg/kg ATB200 + 260 mg AT2221 (single dose)
- 20 mg/kg ATB200 + 130 mg AT2221 (multiple dose) versus 20 mg/kg ATB200 + 260 mg AT2221 (multiple dose)
- 20 mg/kg ATB200 + 130 mg AT2221 (single dose) versus 20 mg/kg ATB200 + 130 mg AT2221 (multiple dose)
- 20 mg/kg ATB200 + 260 mg AT2221 (single dose) versus 20 mg/kg ATB200 + 260 mg AT2221 (multiple dose)

Cohort 3 Subjects:

- 20 mg/kg ATB200 + 260 mg AT2221 (single dose) versus 20 mg/kg ATB200 + 260 mg AT2221 (multiple dose)

Cohort 3 versus Cohort 1 Subjects:

- 20 mg/kg ATB200 + 260 mg AT2221 (multiple dose) versus 20 mg/kg ATB200 + 260 mg AT2221 (multiple dose)
- 20 mg/kg ATB200 + 260 mg AT2221 (single dose) versus 20 mg/kg ATB200 + 260 mg AT2221 (single dose)
- 20 mg/kg ATB200 + 260 mg AT2221 (multiple dose) versus 20 mg/kg ATB200 alone
- 20 mg/kg ATB200 + 260 mg AT2221 (single dose) versus 20 mg/kg ATB200 alone

Following ln-transformation, plasma GAA activity levels and total GAA protein concentration C_{max}, AUC_{0-∞}, and AUC_{0-t}, will be separately analyzed using a fixed effects model with fixed effect terms for treatment or subject group. Point estimates, and their associated 90% confidence

intervals (CIs) will be constructed for the differences, test treatment or subject group, and reference treatment or subject group. The point estimates and their associated 90% CIs will then be back-transformed to provide point estimates and 2-sided 90% CIs for the ratios of test/reference, on the original scale.

A dose proportionality assessment will be performed using the power method for 5, 10, and 20 mg/kg ATB200 in Stage 1 and for 130 and 260 mg AT2221 in Stage 2.

For the dose proportionality analysis, in Stage 1, the reference treatment will be 5 mg/kg ATB200, and the test treatments will be 10 mg/kg and 20 mg/kg ATB200 and, in Stage 2, the reference treatment will be 130 mg AT2221, and the test treatment will be 260 mg AT2221. For the ANOVA comparisons within Stage 2, the reference treatments will be single-dose, and the test treatments will be multiple-dose, and between Stages 1 and 2, the reference treatment will be 20 mg/kg ATB200 alone, and the test treatments will be 20 mg/kg ATB200 + 130 mg AT2221 and 20 mg/kg ATB200 + 260 mg AT2221. For between subject comparisons, the reference group will be Cohort 1 subjects, and test group will be Cohort 3 subjects.

For effect of anti-rhGAA antibody on total GAA protein exposures and plasma clearance, statistical comparisons between after at least 18 months of treatment in Stage 3 versus the first and third doses of treatment with 20 mg/kg ATB200 + 260 mg AT2221 will be performed on estimated plasma total GAA protein AUCs, plasma clearance, and 4-, 6-, 8-, and 12-hour plasma total GAA protein concentrations. PK data from both cohorts will be pooled for the statistical comparisons.

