 - FVC, maximum inspiratory pressure (MIP), maximum expiratory pressure (MEP), and Sniff Nasal Inspiratory Pressure (SNIP)

For Nonambulatory Subjects:

- Muscle Strength Test - Upper Limbs Only
 - MRC and hand-held dynamometer performed for upper limbs only
- PFTs - in subjects without invasive ventilatory support only
 - FVC, MIP, MEP, and SNIP

Patient-reported Outcomes (performed at Baseline and every 3 months in Stage 3):

- FSS
- RHS
- R-PAct Scale
- PROMIS instruments for dyspnea, fatigue, physical functioning, and upper extremity

Exploratory:

- Anti-rhGAA antibodies (total and neutralizing)
- Cross-reactivity of anti-rhGAA antibodies to alglucosidase alfa
- Pro-inflammatory cytokines and other biomarkers of immune system activation
- PD biomarkers: Hex4 and serum CK

Methods of Analysis:

Statistical Methods for PK Parameters:

Details of the analysis methods related to PK parameters will be provided in a stand-alone PK Statistical Analysis Plan (PK SAP). In general, basic descriptive statistics will be provided for all PK parameters.

Cohort 1

- Dose proportionality assessment on GAA activity levels and total GAA protein concentration exposure (C_{max} , AUC_{0-t} , and $AUC_{0-\infty}$) ratios of 5, 10, and 20 mg/kg ATB200 alone.
- Analysis of variance (ANOVA) on GAA activity levels and total GAA protein concentration exposure (C_{max} , AUC_{0-t} , and $AUC_{0-\infty}$) ratios of 20 mg/kg ATB200

alone versus 20 mg/kg ATB200 + 130 mg AT2221, and versus 20 mg/kg ATB200 + 260 mg AT2221.

- Dose proportionality assessment for exposure ratios (C_{max} , AUC_{0-t} , and $AUC_{0-\infty}$) between 130 mg and 260 mg AT2221.
- The effect of immunogenicity results on PK, PD, and safety will be evaluated. Further details will be provided in the Statistical Analysis Plan (SAP).

Cohort 3

- ANOVA on GAA activity levels and total GAA protein concentration exposure (C_{max} , AUC_{0-t} , and $AUC_{0-\infty}$) ratios of 20 mg/kg ATB200 + 260 mg AT2221 in subjects from Cohort 3 versus 20 mg/kg ATB200 alone in subjects from Cohort 1, versus 20 mg/kg ATB200 + 130 mg AT2221 in subjects from Cohort 1, and versus 20 mg/kg ATB200 + 260 mg AT2221 in subjects from Cohort 1.
- ANOVA on AT2221 exposure ratios (which will have the same PK parameters) for 260 mg AT2221 in subjects from Cohort 3 versus 130 mg AT2221 and 260 mg AT2221 in subjects from Cohort 1.

Statistical Methods for Non-PK-Specific Parameters:

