6.4.2. Human Dosing Rationale

To predict ATB200 exposure in humans, a PK model assessing the concentration versus time profile of ATB200 activity was developed based on PK data collected in *Gaa* KO mice and NHPs (Section 6.4.1). The resulting 2-compartment model with linear elimination adequately characterized the concentration versus time profile of ATB200 activity for all dose levels across multiple animal species. The model included a theoretical allometric component accounting for species-specific differences in CL and the volume of distribution (V_d) to predict PK parameters and ATB200 exposure in humans. The PK model also integrated data for rhGAA activity following IV administration of 20 mg/kg alglucosidase alfa. Using the PK model, the predicted CL and V_d of ATB200 in a typical 70 kg human subject are 0.768 L/hr and 2.41 L, respectively. The CL of ATB200 is expected to be approximately 30% faster than the CL of alglucosidase alfa in humans. The faster CL of ATB200 likely reflects its preferential distribution and greater uptake at the site of efficacy resulting from the higher amount of M6P on ATB200, which optimizes drug targeting.

The predicted PK in humans following administration of a single 20 mg/kg IV dose of ATB200 over a 4-hour infusion is shown in [Table 3](#).

Table 3: Predicted PK of Single-dose Administration of ATB200 in Humans

Parameter	Predicted Value
AUC _{0-∞} (mg·hr/L)	1822
C _{max} (mg/L)	423
t _{max} (hr)	4.0
t _{1/2} (hr)	2.17

Abbreviations: AUC_{0-∞} = area under the plasma-drug concentration time curve from Time 0 extrapolated to infinity; C_{max} = maximum observed plasma concentration; IV = intravenous; PK = pharmacokinetic(s); t_{max} = time to reach the maximum observed plasma concentration; t_{1/2} = half-life

Note: PK was predicted for 20 mg/kg of ATB200 administered as a single IV dose over a 4-hour infusion and reflects active protein levels.

The AUC_{0-t} and C_{max} values in humans based on total protein are expected to be similar to those based on rhGAA activity given the toxicokinetic results from the 6-month chronic toxicity study in NHPs. In this study, at the lowest dose tested of 30 mg/kg, similar to the anticipated therapeutic dose of 20 mg/kg, the AUC_{0-t} and C_{max} values for active and total protein were virtually identical (approximately 800 µg·hr/mL for AUC_{0-t} based on active and total protein and approximately 350 µg/mL for C_{max} based on active and total protein).

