6.4.2.4. GAA Protein Using Signature Peptide(s) T09/T50

Total GAA protein in plasma was measured by signature peptides T09 (primary) and T50. Generally, the PK of signature peptide T50 was similar to T09, and therefore confirmed the results of the assay.

In Cohort 1 (ERT-experienced LOPD subjects), total GAA protein by signature peptide T09 exposures (C_{max} and AUC) demonstrated greater than dose-proportional increases during Stage 1 (single-ascending doses of 5, 10, and 20 mg/kg ATB200). Mean AUC for the 20 mg/kg ATB200 alone dose level was similar to translational modeling in the *Gaa* KO mouse to human AUC at the 20 mg/kg dose level (1,822 μ g·h/mL). Co-administration with 130 mg AT2221 resulted in a 19.6% increase in total GAA protein mean AUC. Co-administration with 260 mg AT2221 increased total GAA protein AUCs by 26.3%. These increases were mainly observed during the early terminal phase, as shown by observed increases in the alpha-half-life. Clearance of plasma total GAA protein decreased with dose escalation and remained stable when co-administered with AT2221.

Generally, the PK of 20 mg/kg ATB200 based on plasma total GAA protein was similar between single and multiple doses when co-administered with 130 mg AT2221, and between single and multiple doses when co-administered with 260 mg AT2221.

The plasma total GAA protein PK profile of Cohort 3 (ERT-naïve subjects with LOPD) was generally similar to Cohort 1.

Similar to total GAA protein, in Cohort 1 (ERT-experienced LOPD subjects), total GAA activity exposures (C_{max} and AUC) in plasma demonstrated greater than dose proportional increases during Stage 1 (single-ascending doses of 5, 10, and 20 mg/kg ATB200). However, co-administration with either the low or high dose of AT2221 did not result in any relevant change in total GAA activity mean AUC. Clearance of plasma total GAA activity decreased with dose escalation and remained stable when co-administered with AT2221. Steady-state volume of distribution was consistent across all treatments from approximately 4.5 to 5.9 L.

Generally, the PK of 20 mg/kg ATB200 based on plasma total GAA activity was similar between single and multiple doses when co-administered with 130 mg AT2221, and between single and multiple doses when co-administered with 260 mg AT2221.

The GAA activity PK profile of Cohort 3 (ERT-naïve subjects with LOPD) was generally similar to Cohort 1.

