13.3. Study Treatment Administration

13.3.1. ATB200

The doses of ATB200 are either 5, 10, or 20 mg/kg body weight.

ATB200 does not contain any preservatives. Vials are single-use only. Reconstituted vials should be retained at the site until the study monitor checks accountability.

In all stages, ATB200 is to be administered every 2 weeks as an approximate 4-hour IV infusion (\pm 15 minutes). Changes in the duration of ATB200 infusion due to safety or tolerability issues will be documented. The total volume of infusion is determined by the subject's body weight. Instructions for preparation for infusion, and the volume and rate of infusions will be provided in the Pharmacy manual. Intravenous administration of ATB200 (during all stages) should be performed by qualified study personnel. Any delegation of this responsibility must follow Section 15.4. Rate and duration of infusion must be constant for each infusion. Changes in the rate and/or duration of infusion due to safety or tolerability issues will be documented.

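### The printed PK model for same-subject comparisons has no subject term, and the printed V_ss formula omits the infusion-time correction; check iCSR-1 for both before its PK tables are carried into the final CSR

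*Protocol*

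**What the plan says.** Protocol 12.4.4.1 lists eleven ANOVA comparisons of C_max and AUC for GAA activity and total GAA protein. Seven compare regimens within the same people: six in Cohort 1 and the single- versus multiple-dose comparison in Cohort 3. The other four compare Cohort 3 with Cohort 1. One model description serves them all: after log transformation each parameter "will be separately analyzed using a fixed effects model with fixed effect terms for treatment or subject group". The same section shows that group means cohort: "For between subject comparisons, the reference group will be Cohort 1 subjects, and test group will be Cohort 3 subjects". Two-sided 90% confidence intervals are back-transformed to ratios. The section does not say whether each contrast is fitted separately or all regimens share one model.

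Protocol 12.4.3.2 gives "Steady-state volume of distribution from an IV administration, calculated as" Dose × AUMC/AUC². Section 13.3.1 says "ATB200 is to be administered every 2 weeks as an approximate 4-hour IV infusion", with a 15-minute allowance either way. Section 12.1.1 lists "steady state volume of distribution" among the primary PK parameters for Cohort 1.

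The protocol synopsis defers PK method details to a stand-alone PK SAP, which is not available here. SAP 4.1 and 8.1 both cite protocol 12.4.4.1, for the parameter definitions and the noncompartmental methods respectively. SAP 2 and 8.1 then say that the iCSR-1 PK results will be referenced or copied into the final CSR.

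**The concern.** Cohort 1 takes every regimen in a fixed sequence, so its observations are repeated measures on the same people. A model with treatment as its only term treats them as independent and leaves between-subject variation in the error. Where a subject's exposures are positively correlated across regimens, which is usual, the interval's standard error is too large for the difference it describes. These ratios and intervals are how the plan measures the effect of AT2221 on ATB200 exposure, which is part of a primary PK objective.

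The V_ss expression as printed is correct for a bolus. With an infusion, AUMC/AUC also contains the mean input time, so volume is overstated in proportion to clearance. Protocol 6.4.2.4 reports: "Clearance of plasma total GAA activity decreased with dose escalation and remained stable when co-administered with AT2221". The overstatement would therefore be larger at 5 and 10 mg/kg than at 20 mg/kg.

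Because the final SAP points back to the protocol text and carries the iCSR-1 tables forward, any analysis that followed that text would reappear in the final CSR. Even if the programs were right, readers would be sent to a model and a formula that do not suit the design.

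**Working it through.** **Inputs.** Cohort 1 n = 11 and Cohort 3 n = 5 (protocol Table 8). Infusion time T = 4 h, allowed range 3.75 to 4.25 h (13.3.1). Predicted clearance and volume "in a typical 70 kg human subject are 0.768 L/hr and 2.41 L, respectively" (6.4.2). Within-subject correlation ρ is not given anywhere, so it is varied.

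**The protocol's own figures.** AUC = Dose/CL = (20 × 70)/0.768 = 1822.9 mg·h/L, against 1822 stated. Half-life = ln 2 × 2.41/0.768 = 2.175 h, against 2.17 stated. The clearance used below is therefore the protocol's own.

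**Interval width.** Let σ² be the total log-scale variance. The difference between two regimens in the same n subjects has variance 2σ²(1 − ρ)/n; without a subject term it is estimated as 2σ²/n. Printed width divided by subject-term width is then:

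- separate two-regimen model: t(2n−2)/[t(n−1) × √(1−ρ)], with t at 0.95. For n = 11, t = 1.7247 and 1.8125; for n = 5, t = 1.8595 and 2.1318.
- one model for the five 20 mg/kg regimens and occasions in Cohort 1, equal correlation: t(5(n−1))/[t(4(n−1)) × √(1−ρ)]. For n = 11, t(50) = 1.6759 and t(40) = 1.6839.

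| Width ratio at ρ | 0 | 0.3 | 0.5 | 0.8 | 0.9 |
|---|---|---|---|---|---|
| Two-regimen, n = 11 | 0.95 | 1.14 | 1.35 | 2.13 | 3.01 |
| Five-regimen, n = 11 | 1.00 | 1.19 | 1.41 | 2.23 | 3.15 |
| Cohort 3, n = 5 | 0.87 | 1.04 | 1.23 | 1.95 | 2.76 |

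Setting each ratio to 1 gives the break-even correlation. For n = 11, two regimens: 1 − (1.7247/1.8125)² ≈ 0.094. For n = 5: 1 − (1.8595/2.1318)² ≈ 0.239. For the five-regimen model it is about 0.009.

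**Coverage.** Coverage was found from 200,000 simulated normal data sets per ρ, analysed without a subject term:

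| Coverage (%) at ρ | −0.1 | 0 | 0.1 | 0.3 | 0.5 | 0.8 |
|---|---|---|---|---|---|---|
| Two-regimen, n = 11 | 88.4 | 90.0 | 91.6 | 94.6 | 97.4 | 99.8 |
| Five-regimen, n = 11 | 88.4 | 90.0 | 91.7 | 94.7 | 97.5 | 99.8 |
| Cohort 3, n = 5 | 88.5 | 90.0 | 91.4 | 94.1 | 96.6 | 99.3 |

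In the two-regimen case, adding a subject term returned coverage to about 90% at every ρ from 0 to 0.9 that was tried.

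**Illustration.** Take the 26.3% rise in total protein AUC with 260 mg AT2221 (protocol 6.4.2.4) as a ratio of 1.263, with n = 11 and an assumed total CV of 30%. The 90% interval is 1.02 to 1.57 without a subject term, and 1.08 to 1.48 with one at ρ = 0.5.

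**V_ss.** For a constant-rate infusion, AUMC/AUC equals the disposition mean residence time plus T/2. Hence V_ss = Dose × AUMC/AUC² − Dose × T/(2 × AUC), and the printed form is too high by Dose × T/(2 × AUC) = CL_T × T/2.

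- CL 0.768 L/h, T = 4 h: 0.768 × 4/2 = 1.54 L.
- T from 3.75 to 4.25 h: 1.44 to 1.63 L.
- Assumed CL of 0.5, 1.0 or 1.5 L/h at 4 h: 1.0, 2.0 or 3.0 L.

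Numerical check with an assumed two-compartment model (1400 mg over 4 h, CL 0.768 L/h, V1 2.0 L, Q 0.3 L/h, V2 1.5 L, so true V_ss = 3.5 L): the printed formula returns 5.036 L and the corrected one 3.500 L, a difference of 1.536 L.

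**The case against.** The strongest reply is that protocol section 12 is only an outline and that a PK SAP holds the detail. A term missing from an outline need not be missing from the analysis. Likewise, parameters were to be computed in Phoenix WinNonlin, and the documents do not show whether the reported V_ss came from the printed expression or from an infusion-adjusted output. This stands as a limit: no reported result has been shown to be wrong. It does not rescue the text, because the final SAP names protocol 12.4.4.1 as the description of these methods.

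The effect also depends on an unknown correlation. At zero correlation the printed intervals cover 90%, and in a two-regimen model they are narrower than the subject-term ones. With five subjects the subject term widens intervals until the correlation reaches about 0.24. That is correct, and it is why a range is shown.

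Protocol 6.4.2.4 reports V_ss for GAA activity as consistent across treatments, at roughly 4.5 to 5.9 L. This should be read beside the claim of a dose-dependent excess. It does not contradict it: the range spans 1.4 L, and the formula behind it is unknown. An excess near 1.5 L would matter on that scale.

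Finally, no hypothesis or acceptance limit hangs on these results, V_ss is only summarised, and over-coverage is conservative. That bears on the weight of the point, not on whether it is right. A subject term also leaves treatment confounded with period in the fixed sequence.

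**Conclusion.** Both points hold for the text as printed. The model omits the subject effect that seven of its eleven comparisons need. Over assumed correlations of 0.3 to 0.8, the nominal 90% intervals would actually cover about 94 to 99.8%, and their width would be 1.04 to 2.23 times that of intervals from a model with a subject term, depending on cohort and model. Below zero correlation they would under-cover. The V_ss formula overstates volume by CL_T × T/2: 1.54 L at the predicted clearance, and more where clearance is higher. No percentage error is given, because the documents do not report observed V_ss and clearance for the same analyte and dose. Whether either fault reached iCSR-1 cannot be told from the documents. Since the results are descriptive, the cost would be poorly calibrated intervals and inflated volumes rather than a changed decision.

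**What to change.** 1. Before copying any iCSR-1 PK table, confirm from the PK SAP and program output which model and which V_ss derivation were used, and state both in the final CSR.
2. For all within-cohort comparisons, specify a subject effect, fixed or random, in the log C_max and log AUC model. Keep the group-only model for Cohort 3 versus Cohort 1, where a fixed subject effect would be confounded with cohort.
3. State whether each contrast is fitted separately or all regimens share one model.
4. Define V_ss = Dose × AUMC/AUC² − Dose × T/(2 × AUC), with T the actual infusion duration.
5. Point SAP 4.1 to protocol 12.4.3.2, where the parameter definitions are.
6. Re-run only the tables that followed the printed text.

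The cost is a check of existing programs and output and, if needed, one re-run of the affected tables with the corrected model and formula. No new samples are required.
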